- d. Weekly-based assessments will remain open for up to 3 days (72 hours) and cycle-based assessments will remain open for up to 7 days (168 hours).
- e. Safety reporting will follow applicable regulations and is detailed in Section 16.
- f. Type and duration of treatment for advanced breast cancer used during observation period in this study (including endocrine therapy used in combination with palbociclib) will be collected in both group.
- g. Group 1 only.
- h. “Fatigue” and “General pain” are measured as PRO-CTCAE.
- i. Baseline assessment for PRO data will be conducted after obtaining informed consent and before initiating study treatment.
- j. The observation period in this study will be 6 cycles. In Group 1 (palbociclib plus endocrine therapy), palbociclib is administered for 3 consecutive weeks followed by 1 week off treatment to comprise 1 cycle of 4 weeks. If palbociclib is temporarily interrupted (eg, due to adverse event) and the start of the next cycle is delayed, the duration of one cycle may exceed 4 weeks, then, the observation period may exceed 24 weeks. In Group 2 (endocrine monotherapy), 1 cycle is defined as 4 weeks.
- k. To be assessed at Baseline and End of study. If ECOG performance status is assessed during the observation period, the data will be entered into EDC. If patients discontinue the initiated treatment before completion of 6 cycles (eg, due to disease progression) and switch to another treatment, ECOG performance status will be assessed at end of treatment as well.

PFIZER CONFIDENTIAL

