9.1.3.1. Data sources

Data for this study will be obtained via the following sources:

- **Patient medical information:** The investigator or designated study site staff will record clinical and treatment data from patients' medical records into an eCRF promptly at baseline, during the observational period, and at the end of the observational period. Types of data to be obtained from patient medical records are described in Section 6 "Schedule of Activities".

- **Patient-Reported Outcome data:** All patients will be asked to complete a baseline questionnaire, as well as series of questions at weekly, and cycle-based intervals via a smartphone-based application downloaded onto their smartphones. PRO data entered in smartphone-based application will be transferred into the server hosted by the designated PRO vendor. Two validated PRO instruments will be administered at baseline and weekly-basis (PRO-CTCAE) or cycle-basis (EORTC-QLQ-C30). Appropriate agreements with the copyright owners will be in place for use in this study.
- **Physical Activity data:** All patients will be asked to wear a wearable device to record their physical activity. Physical activity raw data will be uploaded from the device to Actigraph CentrePoint cloud during each site visit.
- **Site characteristics information:** Basic site characteristics, including geographic location, will be collected via Pfizer's internal system, if applicable.

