10. STUDY PROCEDURES

Screening and Baseline period

Study investigators will screen patients for eligibility, obtain informed consent, and enroll patients meeting the eligibility criteria. Informed consent must be obtained before any study specific procedures are performed. Patient eligibility will be reviewed and confirmed by investigator or study site staff before patients are enrolled in the study.

Investigators or study site staff will complete eCRFs to capture demographic, medical history, and treatment information at screening listed in Section 6 SCHEDULE OF ACTIVITIES.

Enrolled patients will download a smartphone-based application for ePRO into their own device (ie, Bring Your Own Device [BYOD]), be provided access to and trained on the use of the application to complete baseline, weekly, and cycle-based assessments for 6 cycles. As for data to be evaluated, see “PRO data via smartphone-based application” in Section 6 “Schedule of Activities”. Patients will complete baseline assessment for EORTC-QLQ-C30 and PRO-CTCAE at study site, if possible.

Investigators or study site staff will assign the wearable device to patients, and patients will be provided with the assigned device and be requested to wear the device at all-times, except of while bathing and sleeping, for 6 cycles. As baseline observation period, it is recommended to wear the device soon after obtaining informed consent until initiating the study treatment. At least 4 days is recommended for baseline observation period to obtain stable baseline data, but treatment schedule of each patient should be prioritized.

Observation Period

PFIZER CONFIDENTIAL

The observation period in this study will be 6 cycles (24 weeks).

In Group 1, palbociclib is administered for 3 consecutive weeks followed by 1 week off treatment to comprise 1 cycle of 4 weeks. If palbociclib is temporarily interrupted (eg, due to adverse event) and the start of the next cycle is delayed, the duration of 1 cycle may exceed 4 weeks, then, the observation period may exceed 24 weeks. In Group 2, one cycle is defined as 4 weeks.

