The PRO-CTCAE is a PRO measurement system that includes a library of questions that measure symptomatic adverse events from the patient perspective. Seventy-eight symptom terms that are common in oncology clinical trials can be evaluable with PRO-CTCAE, and each of symptom terms is assessed relative to one or more distinct attributes, including frequency, severity, and/or interference with usual or daily activities. Responses are provided on a five-point Likert scale. The linguistic and psychometric validation of the questionnaire into Japanese was conducted and Japanese translated version is available through US-NCI webpage.

Fatigue and General pain will be evaluated in this study. Fatigue is one of common adverse event observed in PALOMA studies, and General pain is one of the major symptoms for patients with ABC. Also, it is reported that these two symptoms are frequently underestimated, then these two are selected to evaluate in this study to understand day-to-day effects of ABC treatment on patients in a real-world setting.

Treatment satisfaction

Treatment satisfaction will be evaluated with single item question (eg, “How satisfied are you with your current breast cancer treatment?”). Responses are provided on a five-point Likert scale. Single item question is selected rather than validated questionnaire (eg, Cancer Therapy Satisfaction Questionnaire) considering the burden on patient regarding a number of questions.

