5.2. General Methods

All endpoints will be summarized by descriptive statistics.

As a secondary analysis, we will perform t-test or nonparametric test (if needed) to assess the association between primary endpoints and adverse events and disease progression. **CC1**
[REDACTED]

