6.2. Secondary Endpoint(s)

6.2.1. EORTC-QLQ-C30 scores

- ✓ The same analysis for other 14 scales of EORTC-QLQ-C30 (5 functional scales [physical, role, emotional, cognitive, and social functioning], 8 symptom scales [fatigue, nausea/vomiting, pain, dyspnea, sleep disturbance, appetite loss, constipation, and diarrhea], and financial difficulties scale) are performed as for global health status.
- ✓ Following analyses of 5 functional scales and Global health status scale of EORTC-QLQ-C30 are performed to assess the associations as follows:

When associations for group 1 and 2 were similar, the group 1 and 2 will be pooled.

- Tabulate patients with and without selected investigator-reported AE at each cycle, summarize the mean values of change in EORTC-QLQ-C30 from baseline at each cycle in each tabulated population, and compare the results at Cycle 1 and Cycle 3 using t-test
- Tabulate patients with and without symptom of PRO-CTCAE at each cycle, summarize the mean values of change in EORTC-QLQ-C30 from baseline at each cycle in each tabulated population, and compare the results at Cycle 1 and Cycle 3 using t-test
- Tabulate patients with disease progression during the observation period, and summarize the mean values of EORTC-QLQ-C30 before and after disease progression

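### Change in QLQ-C30 is compared by current PRO-CTCAE symptom without using the baseline symptom score already collected, which attenuates the association when symptoms persist from baseline

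*SAP*

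**What the plan says.** SAP 6.2.1 repeats Protocol 12.5.2. For global health status and the five functional scales, the analyst is to "Tabulate patients with and without symptom of PRO-CTCAE at each cycle". The outcome set against this split is the change score, averaged per cycle within each of the two sets. For testing, the instruction is to "compare the results at Cycle 1 and Cycle 3 using t-test". SAP 6.2.2 carries a similar analysis to the physical activity metrics.

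The general method in SAP 5.2 reads "As a secondary analysis, we will perform t-test or nonparametric test (if needed) to assess the association between primary endpoints and adverse events and disease" (the last word of the sentence, left off here, makes this progressive disease). It names no covariate, and text directly after it is redacted.

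A baseline symptom score exists. Protocol 9.1.3.1 states: "Two validated PRO instruments will be administered at baseline and weekly-basis (PRO-CTCAE) or cycle-basis (EORTC-QLQ-C30"). Protocol section 6, footnote i, fixes the timing: "Baseline assessment for PRO data will be conducted after obtaining informed consent and before initiating study treatment". Protocol section 10 adds: "Patients will complete baseline assessment for EORTC-QLQ-C30 and PRO-CTCAE at study site, if possible". The two symptoms are fatigue and general pain. On the second, Protocol section 11 says: "General pain is one of the major symptoms for patients with ABC".

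No visible text brings the baseline PRO-CTCAE score into this comparison, whether as a covariate, as a stratum or in the definition of the symptom. By contrast, the mixed models for the primary endpoints (SAP 6.1.1.1 and 6.1.2.1) do adjust for the baseline value of their own outcome.

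**The concern.** The two sides of the comparison are on different footings. Change from baseline removes whatever the symptom was already doing to quality of life before treatment, while the grouping takes no account of whether the symptom was already there. Persisting symptoms put patients with little expected change into the symptomatic set, and resolved symptoms put improvers into the symptom-free set. Both movements pull the contrast toward zero.

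This is the planned answer to a stated secondary objective (Protocol 8.1, SAP 2.1). A small difference could be read as showing that fatigue and pain matter little to daily life, when part of the reason is how patients were sorted. A rank test, which SAP 5.2 allows as an alternative, uses the same sorting and does not help.

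**Working it through.** The documents state no effect size, power or error rate for this comparison, so there is no planned figure to reproduce. The check is a closed-form calculation.

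**Inputs from the documents**
- Exposure, outcome and test: SAP 6.2.1.
- Illustrative effect D = 10 points, the change that SAP 3.1 treats as clinically significant.
- Total of 100 patients, with about 20 to 80 per group (Protocol 9.1).

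**Assumed inputs** (not in the documents)
- b, baseline prevalence of the symptom: 0.2 to 0.6.
- p, probability that a baseline symptom is present at the cycle: 0.6 to 0.95.
- q, probability of the symptom at the cycle in patients without it at baseline: 0.2 to 0.4.
- For power only: SD of change 20, two-sided 0.05.

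**Model.** Let S0 and St be symptom yes/no at baseline and at the cycle. If the symptom lowers the score by D whenever present, change = -D(St - S0) + error. Then:
- P(St = 1) = bp + (1 - b)q
- mean change, with symptom = -D(1 - b)q / [bp + (1 - b)q]
- mean change, without symptom = +D b(1 - p) / [1 - bp - (1 - b)q]
- size of contrast = D{1 - [P(S0 | with) - P(S0 | without)]}

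The contrast is smaller than D whenever p exceeds q.

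**One case in full** (b = 0.4, p = 0.8, q = 0.2). P(St = 1) = 0.32 + 0.12 = 0.44. With symptom: -10 x 0.12/0.44 = -2.7. Without: +10 x 0.08/0.56 = +1.4. The contrast is -4.2 against a true -10.

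| b | p | q | With | Without | Contrast |
|---|---|---|---|---|---|
| 0 | any | 0.2 or 0.4 | -10.0 | 0.0 | -10.0 |
| 0.2 | 0.6 | 0.4 | -7.3 | +1.4 | -8.7 |
| 0.2 | 0.8 | 0.4 | -6.7 | +0.8 | -7.4 |
| 0.4 | 0.8 | 0.4 | -4.3 | +1.8 | -6.1 |
| 0.4 | 0.8 | 0.2 | -2.7 | +1.4 | -4.2 |
| 0.4 | 0.95 | 0.2 | -2.4 | +0.4 | -2.8 |
| 0.6 | 0.95 | 0.2 | -1.2 | +0.9 | -2.1 |

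Over b from 0.2 to 0.6, the contrast runs from 8.7 down to 2.1 points, so 87% to 21% of the effect remains.

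**Adjusted analysis.** In simulation (1,500 runs per setting), regressing change on current and baseline symptom gave close to 10 points in every setting. At b = 0.4, p = 0.8, q = 0.4, power for the t-test versus the adjusted model was 31% versus 61% at N = 100, 25% versus 51% at N = 80, and 10% versus 15% at N = 20.

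**A tempting alternative.** Suppose patients with a new symptom are compared with all others. At b = 0.4, p = 0.8, q = 0.2, the new-symptom share is 0.6 x 0.2 = 0.12, and the comparator mean is +10 x 0.08/0.88 = +0.9. The contrast is -10.9, an overshoot. For prevalence 30-50%, persistence 60-80% and onset 10-20%, it is 1.06 to 1.22 times the true effect. The exposed set is then only 5-14% of patients: 1 to 3 of 20, or 4 to 11 of 80.

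**The case against.** The strongest reply is that the plan promises only an association. The objective is worded that way, Protocol section 14 warns against causal attribution, and SAP 5.1 rules out decisions based on tests. Mean change by current symptom status is a legitimate description. This stands, and it confines the point to interpretability. A reader might infer that the t-test fails to deliver a causal effect the plan had undertaken to estimate; the documents give no such undertaking.

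A reader might also infer that the association will be hidden, with a 10-point effect reading as about 3 to 6. That range (29-61% remaining) needs onset of only 10-20%, with prevalence 30-50% and persistence 60-80%. Raising onset to 30-40% leaves about 50-83%. The background trials report fatigue in 39.6% and 44.1% of patients on palbociclib and in 28.4% and 31.4% on placebo. Those are whole-trial adverse event rates rather than per-cycle onset, but they give no reason to cap onset at 20%. Nor do the documents show that baseline symptoms will be common: general pain is called a major symptom of the disease, yet eligibility requires ECOG 0-1.

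The yes/no model also ignores grading. PRO-CTCAE has five response levels, and a patient who moves from mild to severe may have a real decline that the formula sets to zero, so the attenuation may be overstated.

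Finally, parts of the SAP are redacted. The supportable statement is that no visible text uses the baseline score.

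**Conclusion.** The point holds as attenuation of a secondary, descriptive association. The direction needs only that baseline and current symptoms are positively related. The size is not known from the documents: under the assumed ranges, 21-87% of a true effect remains, and there is no loss if no patient has the symptom at baseline. The calculation rests on a binary symptom with a constant additive effect. No primary conclusion is affected. The change is still worth making, because the missing covariate is scheduled to be collected and the SAP already adjusts its primary models for baseline.

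**What to change.** In SAP 6.2.1, keep the table of mean change by current symptom. Replace the t-tests at Cycles 1 and 3 with a linear model of QLQ-C30 change on current PRO-CTCAE symptom, with baseline PRO-CTCAE score and baseline QLQ-C30 score as covariates. In SAP 6.2.2, do the same for each activity metric, using its own baseline value in place of the QLQ-C30 score. While editing, state the score that counts as having a symptom and how the weekly PRO-CTCAE entries reduce to one status per cycle; the visible text gives neither.

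Do not substitute a split of new or worsened symptom against everyone else: patients whose symptom resolved would stay in the comparator and inflate the contrast.

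The cost is SAP wording, with no new data. Patients lacking a baseline PRO-CTCAE drop out of this analysis, and one or two degrees of freedom are spent, which is felt mainly if a group is near 20. Protocol 12.5 asks for an amendment only for major changes to the primary endpoints or their analyses, so a SAP revision should suffice.

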8. RESEARCH QUESTION AND OBJECTIVES

8.1. Research Objectives

Primary objective

Assess change in (1) PRO as measured by EORTC-QLQ-C30 collected via smartphone-based application and (2) physical activity as measured by wearable device in Japanese patients with HR+/HER2- advanced breast cancer receiving below endocrine-based treatment as first or second line setting:

1. Palbociclib plus endocrine therapy (Group 1) or
2. Endocrine monotherapy (Group 2)

NOTE: The study is not intended to compare outcomes between the two groups as primary objective.

Secondary objectives

The following research objectives will be addressed separately for both Group 1 and 2.

- Assess the association between change in EORTC-QLQ-C30 and physical activity versus investigator-reported adverse event (AE)
- Assess the association between change in EORTC-QLQ-C30 and physical activity versus patient-reported symptom as measured by PRO-CTCAE collected via smartphone-based application
- Assess the association between change in EORTC-QLQ-C30 versus change in physical activity

- Assess the association between change in EORTC-QLQ-C30 and physical activity versus disease progression
- Assess the feasibility of collecting physical activity data with wearable device in Japanese patients with advanced breast cancer
- Assess patient's treatment satisfaction (collected as single item via smartphone-based application)
- Evaluate concordance and discordance between investigator-assessed AE versus PRO-CTCAE
- Characterize patients with HR+/HER2- ABC initiating each group treatment (eg, baseline patient demographics and clinical characteristics)

The following research objectives will be addressed Group 1 only.

- Describe dosing patterns (eg, dose reduction, dose interruptions, cycle delay)

CCI

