Patients will complete PRO assessment in weekly, and cycle-basis and wear the wearable device for 6 cycles. At the patients' regular clinical visits at approximately 30 day interval, they will bring the device worn in the past period, and study site staff will confirm if the returned wearable device is still functional and upload the physical activity data through Actigraph application (ie, ActiSync) into the Actigraph cloud system (ie, Actigraph CentrePoint). Detailed information will be included in User Manual and training for Actigraph CentrePoint for the sites. For the PRO and physical activity data collected from the patient, the data entry status or wearing status will be confirmed, but the data itself will not be confirmed. In addition, investigators or study site staff will complete eCRF to capture treatment changes and clinical outcomes (eg, adverse event) for 6 cycles after enrollment listed in SCHEDULE OF ACTIVITIES.

If a patient has not entered any data through ePRO application for 4 consecutive weeks or if a patient has not worn the wearable device for 4 consecutive weeks, the study site staff will be notified and asked to reach out to the patient.

Even if patients discontinue the initiated treatment before completion of 6 cycles and switch to another treatment, to assess association between change in QoL and physical activity versus disease progression, data collection (including PROs [EORTC-QLQ-C30 and PRO-CTCAE] and physical activity evaluation, EDC data entry) will continue to the end of the study (ie, 24 weeks after initiation of initial treatment).

End of Study

End of study is defined as end of 6 cycles of initiated treatment. If patients discontinue the initiated treatment before completion of 6 cycles (eg, due to disease progression) and switch to another treatment, end of study will be end of 24 weeks after initiation of initial treatment.

Investigators or study site staff will complete CRF to capture End of Study information listed in Section 6 SCHEDULE OF ACTIVITIES.

Patients will return the wearable device to study site staff. Study site staff will stop the collection of the physical activity data via configuration in Actigraph system (ie, Actigraph CentrePoint). Detailed information will be included in User Manual and training for Actigraph CentrePoint for the sites.

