6.2.2. Physical activity metrics

- ✓ The same analysis for other physical activity metrics (steps, MVPA time) is performed as for Sedentary time.
- ✓ The similar analyses of each physical activity metrics, as same as that for EORTC-QLQ-C30, are performed to assess the associations.

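### The progression objective rests on before/after means in progressors only, with no control for time on study, and SAP 5.2 announces a test that 6.2.1 does not specify

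*SAP*

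**What the plan says.** The objective in Protocol 8.1, repeated in SAP 2.1, is: "Assess the association between change in EORTC-QLQ-C30 and physical activity versus disease progression". Protocol 10 and note c of the Schedule of Activities continue collection up to 24 weeks in patients who stop the initial treatment and switch. The stated reason is "to assess association between change in QoL and physical activity versus disease progression".

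The analysis in SAP 6.2.1, worded identically in Protocol 12.5.2, is: "Tabulate patients with disease progression during the observation period, and summarize the mean values of EORTC-QLQ-C30 before and after disease progression". For the device data, SAP 6.2.2 says: "The similar analyses of each physical activity metrics, as same as that for EORTC-QLQ-C30, are performed to assess the associations".

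SAP 5.2 goes further: "we will perform t-test or nonparametric test (if needed) to assess the association between primary endpoints and adverse events and disease progression". It does not say whether the test is paired or two-sample, or what is compared with what. The text straight after that sentence is redacted.

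The neighbouring adverse-event item in 6.2.1 is built differently. It starts "Tabulate patients with and without selected investigator-reported AE at each cycle, summarize the mean values of change in EORTC-QLQ-C30 from baseline" and ends with a t-test at Cycles 1 and 3. The PRO-CTCAE item has the same form.

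**The concern.** The objective concerns the association of change with progression. The planned summary uses raw values, in one subset, on either side of an event. Three things are missing from the visible text.

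- **A reference for time.** Values after progression always come later in the study than values before it. Any ordinary trend on treatment is therefore counted as an effect of progression.
- **A fixed set of patients.** Nothing limits the two means to patients who contribute to both, so the means can differ because the respondents differ.
- **Windows and a test.** There are up to seven QLQ-C30 assessments per patient, and nothing says which count as before and which as after. The test promised in 5.2 has no counterpart in 6.2.1.

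Patients go on answering questionnaires and wearing the device after a treatment switch for this question. The number reported could be off by a material part of the 10 points that the documents call clinically significant (Protocol 11, SAP 3.1).

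**Working it through.** The documents give no sample size, power or expected count for this analysis, so there is no figure of the plan's own to reproduce. The calculations below are illustrations.

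**1. How many patients are involved**

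Inputs: Japanese median PFS in Protocol 7, which is 22.2 months (palbociclib) and 13.8 months (control) as first-line therapy, and 13.6 and 11.2 months after prior endocrine therapy. Group sizes are 20 to 80 (Protocol 9.1) or about 50 each (SAP 2.2). Assumption: exponential PFS.

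24 weeks = 24 × 7 / 30.4375 = 5.52 months. Proportion by week 24 = 1 − 2^(−5.52 / median).

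- First line: 15.8% with palbociclib, 24.2% with monotherapy.
- After prior endocrine therapy: 24.5% and 28.9%.

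Lowest total per 100: 80 × 0.158 + 20 × 0.242 = 12.7 + 4.8 = 17.5. Highest: 20 × 0.245 + 80 × 0.289 = 4.9 + 23.1 = 28.0. The 50/50 split gives 7.9 + 12.1 = 20.0 and 12.3 + 14.5 = 26.8. A group of 20 would hold only about 3 to 6 progressors.

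**2. What time trend alone does**

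Simulation among patients progressing before week 24. Visits are at weeks 0, 2, 6, 10, 14, 18 and 22 (baseline, then Day 15 of each 4-week cycle). Assumptions: a linear drift unrelated to progression, between-patient SD 18 and within-patient SD 12 (the SDs do not affect the expected difference). Medians of 22.2, 13.8 and 9.2 months were used, and the choice hardly matters. With **zero** true effect of progression, after minus before is:

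| Assumed drift over 24 weeks | All observations pooled | Within-patient averages | Adjacent visits |
|---|---|---|---|
| 0 | about 0 | about 0 | about 0 |
| +5 | 1.9 to 2.2 | 2.7 to 2.8 | 0.7 to 0.9 |
| +10 | 4.1 to 4.2 | 5.5 to 5.6 | 1.6 to 1.7 |
| −10 | −4.3 to −4.1 | −5.5 | −1.6 to −1.5 |

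The within-patient column shows that pairing alone does not remove the problem. The last column shows how much depends on the undefined windows: adjacent visits are mostly 4 weeks apart, and 10 × 4/24 = 1.7.

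With a true effect of −10 and medians of 22.2 and 13.8 months, a +10 drift gives a pooled contrast of about −5.9, and a −10 drift gives about −14.2.

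**3. What changing respondents can do**

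In the same simulation, 7 to 8% of progressors have no visit after progression, before any non-response. As an assumed example, let 5 of 15 progressors stop responding and differ by 10 points from the rest. The after mean then shifts by 5/15 × 10 = 3.3 points: upwards if the non-responders were worse off, downwards if they were better off.

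**The case against.** The study is declared descriptive and hypothesis-generating (Protocol 12.1 and 14, SAP 5.1), this objective is secondary, and limits on causal attribution are acknowledged. A before/after summary is a legitimate crude description, and redacted text may hold more. This stands in part: it limits the point to the visible text and rules out saying that the plan yields nothing. It does not remove the point. A descriptive association still needs a reference and defined windows, the adverse-event and PRO-CTCAE items have comparison groups, and 5.2 promises a test.

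Four stronger readings are tempting, and the documents do not support them.

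- **That the means are unpaired and a standard error is therefore wrong.** The documents are silent on pairing, and 6.2.1 plans no standard error for this item.
- **That the bias hides harm.** Sicker patients may drop out more, but nothing in the documents shows it, and drift can act in either direction.
- **That up to 64% of a group progresses.** That comes from the overall-trial median of 3.8 months (1 − 2^(−5.52/3.8) = 0.635). The same section gives 11.2 months for Japanese patients, and this study is Japanese.
- **That the summary cannot inform the objective at all.** It gives a contrast within progressors, though a confounded one.

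**Conclusion.** The point holds in a limited form. As written, the progression analysis gives a crude contrast within progressors that mixes progression with time on study and with changes in who responds. SAP 5.2 and 6.2.1 do not match on whether, or how, progression is tested.

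Under an assumed 10-point drift over 24 weeks the spurious difference is about 4 to 6 points for pooled observations or within-patient averages, and under 2 points for adjacent visits. With no drift it is zero. The drift is an assumption, since the documents give no figure for it.

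The count of roughly 17 to 28 progressors per 100 is approximate. It assumes exponential PFS, PFS also counts deaths, and the medians come from small trial subgroups.

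**What to change.** In SAP 6.2.1, carried to the device data through 6.2.2:

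1. Report the within-patient change from before to after progression, with a 95% CI, only in patients with both values. State which assessments count as before and as after.
2. Add a time-varying progression indicator to the repeated-measures models already planned in SAP 6.1.1.1 and 6.1.2.1, using all patients and adjusting for cycle or week. Separate within-patient from between-patient effects, for instance by patient-mean centring; a plain indicator in an all-patient model would blend the two. Report the coefficient and 95% CI for global health status and for sedentary time.
3. Align SAP 5.2 with this, so that the method named there is the one specified in 6.2.1.

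Cost: SAP wording and a small extra analysis. Protocol 12.5 reserves amendments for major changes to the primary endpoints, so none should be needed. The Schedule of Activities lists disease progression as CRF data but does not mention a date, so confirm that one is recorded. Monitoring times are at the physician's discretion, so the date will be that of detection.

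Limits to state in the report:

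- The model takes the time trend as common to progressors and non-progressors.
- The coefficient describes progression together with any treatment switch, which this design does not separate.
- Precision will be poor. With 13 progressors, an assumed SD of 20 and within-patient correlation of 0.3, 0.5 or 0.7, the paired 95% CI half-width, t × SD × √(2(1 − ρ)/n), is 14.3, 12.1 or 9.4 points.
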